6.6.4. Vital Signs and Physical Examinations

Vital signs include: Height (cm), Weight (kg), Body Mass Index, Systolic Blood Pressure (mmHg), Diastolic Blood Pressure (mmHg) and Heart Rate (beats/min).

Height is assessed at Screening (main study); Weight is assessed at Month 6, Month 9, Month 12, as well as at M3 ExtFU and M6 ExtFU visits. Other Vital Signs are assessed at every monthly visit during the extension treatment period and at Month 1, 3 and 6 from the extension follow-up period.

Physical Examination was to be assessed Month 6, Month 9, Month 12, as well as at M3 ExtFU and M6 ExtFU visits.

The actual value, change from baseline and change from baseline 2 (only for the subjects who are in the placebo arm in the main study) for each on-study evaluation will be summarized by treatment group for vital signs.

By-subject listings of vital sign measurements will be presented in data listings.

Physical examination results at each time point will be summarized by treatment group; Shifts from Baseline and shift from baseline 2 (only for the subjects who are in the placebo arm in the main study) in physical examination findings to each on study visit will also be presented.

All physical examination findings will be presented in a data listing.

6.6.5. **Electrocardiogram**

Local 12-lead ECG readings of QTcF are performed at every monthly visit during the extension treatment period, as well as Months 1,3 and 6 from the extension follow-up period.

Baseline will be defined as the highest QTcF value prior to first dose of the main study.

Baseline 2 will be defined as the highest QTcF value prior to first active dose of the extension study from screening to Month 6 (only for subjects in the placebo arm of the main study).

The actual value, change from baseline and change from baseline 2 (only for the subjects who are in the placebo arm in the main study) of ECG results will be summarized descriptively, as well as the number and percent of subjects with normal, abnormal and clinically significant abnormal results at each study visit by treatment group.

All ECG data for each subject will be provided in data listings.

6.6.6. **Concomitant Medications**

Concomitant medications will be coded using the WHO Drug dictionary. Frequencies and percentages will be presented for each treatment group and overall by the first level anatomical main (ATC 1) group and preferred name. Vitamin D and Calcium supplementation as collected in the eCRF at each visit will be summarized as well.

All medications administered between the date of the Month 6 visit and the date of the last dose of extension study drug, inclusive, (i.e., all medications starting or ongoing during the time interval) are concomitant to the extension treatment period.

Concomitant medications tables will be presented for the following periods: Month 6 to Month 12 (Extension treatment period) and Month 12 to Month 6 ExFU (Extension follow-up period) as defined in section 5.2.1.

The use of prior and concomitant medications will be included in a by-subject data listing.

6.6.7. **Transvaginal Ultrasound (TVUS)**

TVUS was to be performed at Month 6, Month 9, Month 12, as well as Month 3 and Month 6 of Extension Follow-up period.

The actual value, change from baseline and change from baseline 2 (only for subjects in the placebo arm in the main study) will be summarized by treatment group for uterus length, width, and depth in mm and corresponding uterine volume in cm3, endometrium thickness in mm.

The number and percentage of subjects with ovarian endometrioma with a diameter of 7 cm or greater, and development of any uterus, left ovary or right ovary abnormality over time will be presented by treatment group.

All TVUS data for each subject will be provided in data listings.

6.6.8. **Other Examinations**

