Liver function tests: following the Food and Drug Administration (FDA) guidance on drug-induced liver injury (8), subjects who have an elevation of hepatic enzymes are to be withdrawn immediately from treatment if:

- ALT or AST $>8xULN$
- ALT or AST $>5xULN$ for more than 2 weeks
- ALT or AST $>3xULN$ and (TBL $>2xULN$ or INR >1.5)
- ALT or AST $>3xULN$ with the appearance of fatigue, nausea, vomiting, right upper quadrant pain or tenderness, fever, rash, and/or eosinophilia ($>5\%$)

Withdrawn subjects will be followed up until hepatic parameters return to normal.

ECG: subjects who have a QTcF > 500 ms or increase > 60 ms from the highest value prior to the first dose in the main study will have to be withdrawn from study treatment and followed up until return to QTcF < 480 ms or – if not reached after 3 months of treatment cessation- be referred to a cardiologist. They will enter the 6-month Follow-Up Period and undergo the follow-up ECGs according to the schedule of events.

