Appendix A. Schedule of study assessments – Treatment Period

Schedule of study assessments – Treatment Period							
Timing ¹	Treatment Period						
	M6 ²	M7	M8	M9	M10	M11	M12
Informed Consent	X						
Inclusion-Exclusion criteria	X						
Physical examination (including weight)	X			X			X
Columbia-Suicide Severity Rating Scale	X	X	X	X	X	X	X
ECG ³	X	X	X	X	X	X	X
Vital signs	X	X	X	X	X	X	X
Urine pregnancy test	X	X	X	X	X	X	X
Endometrium TVUS	X			X			X
Gynecological examination	X			X			X
Endometrial biopsy	X ⁴						X ⁴
Manual breast examination	X						X
Clinical laboratory & urinary protein dipstick	X ⁵	X	X	X ⁵	X	X	X ⁵
BMD by DXA	X			X ⁶			X
Adverse events	X	X	X	X	X	X	X
Concomitant medication	X	X	X	X	X	X	X
Contraceptive dispensing and counselling	X	X	X	X	X	X	X
Permitted analgesic prescribing/dispensing	X	X	X	X	X	X	X
Vitamin D and calcium dispensing	X	X	X	X	X	X	X
Subject eDiary completion check	X	X	X	X	X	X	X

¹ All visits should take place at the end of the defined period (i.e. M7 visit should be scheduled at the end of Month 7, M8 visit should be scheduled at the end of Month 8, etc.). All visit dates should be calculated from the date of Day 1 visit (in the main study). A month is defined as 28 days/4 weeks. Visits should be scheduled ± 3 days (-3/+ 2 days for Month 7 visit) from the calculated date.

² All Month 6 assessments except informed consent and inclusion/exclusion criteria would have been performed as part of the main study (18-OBE2109-003 - Edelweiss 3).

³ ECG should be performed at about the same time but before the PK sample

⁴ If endometrium thickness in TVUS is ≤ 5 mm, no endometrial biopsy will be necessary.

⁵ Overnight fasting is required.

⁶ Only for subjects who met the following criterion at any site on the M6 DXA scan: $-2.5 < Z\text{-score} \leq -1.5$

Schedule of study assessments – Treatment Period (cont'd)

Schedule of study assessments – Treatment Period							
Timing ¹	Treatment Period						
	M6 ²	M7	M8	M9	M10	M11	M12
IMP accountability	X	X	X	X	X	X	X
Dispense linzagolix/placebo kit	X	X	X	X	X	X	
Dispense ABT/placebo kit	X			X			
EHP-30, EQ-5D-5L and PROMIS ³	X	X		X			X
mPGIS, PGIC, HRUQ and HRPQ ³	X	X	X	X	X	X	X
SSIQ and PSIQ ³	X						X
Blood sample for PK ⁴	X	X	X	X	X	X	X
E2, LH, P4	X	X	X	X	X	X	X
SHBG	X			X			X
Bone biomarkers	X			X			X

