¹ All visits should take place at the end of the defined period (i.e. M7 visit should be scheduled at the end of Month 7, M8 visit should be scheduled at the end of Month 8, etc.). All visit dates should be calculated from the date of Day 1 visit (in the main study). A month is defined as 28 days/4 weeks. Visits should be scheduled \pm 3 days from the calculated date.

² All Month 6 assessments except informed consent and inclusion/exclusion criteria would have been performed as part of the main study.

³ ClinROs (PSIQ and HRUQ) will be administered to the subject by the site staff and the responses will be filled in the eDiary. ePROs (EHP-30, EQ-5D-5L, PROMIS, PGIS, PGIC, HRPQ and SSIQ) will be filled in by the subject in the eDiary.

⁴ PK samples should be taken after the ECG and before the daily dose of IMP.

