6.2. General Statistical Methods

6.2.1. **General Methods**

All output will be incorporated into Microsoft Excel or Word files, sorted and labeled according to the International Conference on Harmonisation (ICH) recommendations, and formatted to the appropriate page size(s).

Tabulations will be produced for appropriate demographic, baseline, efficacy, pharmacokinetic and safety parameters.

The analyses will be performed on 4 treatment groups (taking into account the treatment taken in the main study):

- linzagolix 75 mg / linzagolix 75 mg
- linzagolix 200 mg with ABT / linzagolix 200 mg with ABT
- Placebo / linzagolix 75 mg (subject receiving placebo in main study and treated with linzagolix 75 mg in extension study)
- Placebo / linzagolix 200 mg with ABT (subject receiving placebo in main study and treated with linzagolix 200 mg with ABT in extension study)

For continuous data and for ordered categorical data, if appropriate, the number of non-missing observations, mean, standard deviation, median, first and third quartiles, minimum and maximum will be calculated, including for change from baseline when applicable.

The baseline mean will be calculated for all subjects based on the Extension Safety Analysis Set

For efficacy endpoints and BMD, a baseline mean will also be calculated for each visit using the baseline data for the subset of subjects who attended that visit, such that the same subjects contribute to the mean for the visit and the mean for the corresponding baseline values. Summary

CRS-BS-TP-000005 V 2.0

statistics will be based primarily on non-missing values. For ordered categorical data and nominal data, absolute counts and relative frequencies (in %) will be calculated.

Raw and derived data will be listed.

6.2.2. **Definition of Baseline**

The baseline will be described in two ways:

- Main Baseline (named Baseline), defined in the Statistical Analysis Plan of the main study and calculated according to first dose of IMP taken during the main Study.
- Second Baseline (named Baseline 2), defined as the last assessment before the first active dose of IMP during the extension study. For efficacy endpoints based on daily diary data, the Baseline 2 will be based on the last 28 days prior to and including last treatment administration in main study.

The baseline 2 will be calculated only for the subjects who are in the placebo arm (actual arm) in the main study.

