Demographics and baseline characteristics recorded at baseline in the main study will be summarized by treatment group and overall using descriptive statistics.

Demographics and baseline data include Age (years), Gender, Ethnicity, Race, Height (cm), Weight (kg), Body Mass Index (kg/m2), Systolic Blood Pressure (mmHg), Diastolic Blood Pressure (mmHg), Heart Rate (beats/minute), QTc interval (Fridericia) (ms).

BMI is auto-calculated, defined as: Weight (kg)/(Height(m)*Height(m)).

Demographic and Baseline data will be provided in data listings.

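### SAP 6.6.5 measures mean QTcF change from the highest pre-dose value, which biases the change downward for Baseline 2, and for Baseline wherever a subject has two or more differing pre-dose ECGs

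*SAP*

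**What the plan says.** SAP 6.6.5 (Electrocardiogram) sets two reference values for QTcF. The first is: "Baseline will be defined as the highest QTcF value prior to first dose of the main study". The second, for subjects on placebo in the main study, is: "Baseline 2 will be defined as the highest QTcF value prior to first active dose of the extension study from screening to Month 6". For every group and visit, the actual value and the changes from both baselines "of ECG results will be summarized descriptively, as well as the number and percent of subjects with normal, abnormal and clinically significant abnormal results". SAP 6.2.1 includes the mean among the statistics reported for change from baseline. Neither document takes a maximum after baseline; each visit contributes its own reading.

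SAP 6.2.2 gives a different general rule: "Second Baseline (named Baseline 2), defined as the last assessment before the first active dose of IMP during the extension study". Neither 6.6.5 nor SAP Section 7 (changes to planned analyses) explains why ECGs depart from it.

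The highest pre-dose value appears elsewhere as the reference for an individual withdrawal criterion. Protocol 10.7.2.1 refers to an "increase > 60 ms from the highest value prior to the first dose in the main study".

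**The concern.** A reference that suits a criterion applied to one subject at a time has been carried into group summaries. A single visit reading is set against the largest of several earlier readings, so ordinary reading-to-reading variation alone produces a negative expected change. On a safety variable this error is in the unsafe direction.

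QT prolongation is a named safety objective (Protocol 6.2). Protocol 5.5.3 calls the known effect borderline, exceeding the threshold of concern by less than 2 msec, so an offset of a few milliseconds could hide an effect of the size in question. The extension has no concurrent placebo arm in which the same offset would show.

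The two change columns are also not comparable. The window for Baseline lies inside the window for Baseline 2, so Baseline 2 can never be the lower of the two. In the same switchers, change from Baseline 2 can therefore never exceed change from Baseline.

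**Working it through.** The plan gives no figure to reproduce, so the check has three steps.

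**1. How many readings enter each maximum (k)?**
- Baseline: the main-study ECG schedule is not in the documents, so k is unknown. If k = 1, the maximum is the single value and the bias is 0.
- Baseline 2: at least two. SAP 6.3.3 lists QTcF among the main-study baseline data, so one pre-treatment reading exists. Protocol Appendix A schedules an ECG at Month 6, and its footnote says "All Month 6 assessments except informed consent and inclusion/exclusion criteria would have been performed as part of the main study". That ECG precedes the first active dose: "PK samples should be taken after the ECG and before the daily dose of IMP". If the main study had ECGs at screening, Day 1 and six monthly visits, k would be 8; this is an assumption.

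**2. Direction.** A maximum is never below the last or the mean of the same readings, and it exceeds the mean whenever they differ. Each subject's change from the highest value is therefore no larger than her change from the last or mean value. This needs no distributional assumption.

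**3. Size.** Assume normal readings with no drug effect, where SD is the spread of a single reading and ρ is the correlation between readings in one subject. The within-subject spread is SD × √(1 − ρ), and

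expected downward bias = SD × √(1 − ρ) × E[max of k standard normals].

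E[max] is 0, 0.564, 0.846 and 1.424 for k = 1, 2, 3 and 8. Neither SD nor ρ is in the documents. The assumed ranges are SD 5 to 12 ms and ρ 0 to 0.7, which give a within-subject spread from 5 × √0.3 = 2.7 ms up to 12 ms.

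| SD (ms), ρ | k = 1 | k = 2 | k = 3 | k = 8 |
|---|---|---|---|---|
| 5, 0.7 | 0 | 1.5 | 2.3 | 3.9 |
| 5, 0 | 0 | 2.8 | 4.2 | 7.1 |
| 12, 0.7 | 0 | 3.7 | 5.6 | 9.4 |
| 12, 0 | 0 | 6.8 | 10.2 | 17.1 |

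Example: 5 × √0.3 × 0.564 = 1.5 ms, and 12 × 1 × 0.564 = 6.8 ms.

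Built-in gap between change from Baseline and change from Baseline 2 in the same switchers:
- 1 versus 2 readings: the k = 2 column, 1.5 to 6.8 ms.
- 2 versus 8 readings: 0.859 × SD × √(1 − ρ), which is 2.4 ms (SD 5, ρ 0.7) to 10.3 ms (SD 12, ρ 0).

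A simulation with no drug effect (400,000 subjects per case, independent readings, SD 10 ms) gave mean changes from the highest value of −5.66 ms at k = 2 and −14.24 ms at k = 8. At k = 2 a true rise of 5 ms would be reported as 5 − 5.66 = −0.66 ms. With the last or the mean pre-dose value as baseline, the mean change was 0.0 ms at every k.

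**The case against.** The strongest reply concerns scope. The study's focus is on subjects who had active treatment in the main study, and Baseline 2 is not computed for them. For Baseline, no bias can be demonstrated because the number of pre-dose ECGs is unknown. What can be shown from the documents is limited to one descriptive column for placebo switchers, who are a secondary objective. That limit stands. It does not rescue the Baseline 2 column, and a rule that picks the highest value has an effect only where several values exist.

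Second, SAP 6.6 and the V3.0 changes say main-study data will also appear in the safety tables, and off-drug ECGs are taken in follow-up. A careful reader might therefore see an offset in change from Baseline. This is a partial check; it is not a concurrent control and does not repair Baseline 2.

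Third, the documents place the question of a few milliseconds in a dedicated QT study with placebo and a positive control, while this study uses local readings and categorical limits. This lowers the stakes, but change in ECG is still a listed safety endpoint here.

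Fourth, the highest value matches the protocol's own withdrawal criterion and may carry over the main-study SAP, which is not available. That may explain the choice but does not make it suitable for mean change. SAP 6.6.5 plans no count against the >60 ms criterion, the one table the highest value would suit.

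Finally, the size rests on assumptions. A reader who takes 5 to 12 ms as already within-subject should use the ρ = 0 rows, where the k = 2 bias is 2.8 to 6.8 ms.

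**Conclusion.** The concern holds. Mean change from Baseline 2 is biased downward because at least two readings are eligible for the maximum. Mean change from Baseline is biased in the same way wherever a subject has two or more differing pre-dose ECGs, and not at all with one. The direction is certain. The size, 1.5 to 6.8 ms at the documented minimum of two readings and more with further readings, depends on the assumed SD, correlation and normal readings.

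This should be corrected, but its reach is limited. Actual values, abnormality counts and listings are unaffected, change from Baseline uses one rule in all four groups, and no hypothesis test or subject-level stopping rule depends on mean change.

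**What to change.** Replace the baseline definitions in SAP 6.6.5 with text such as: *For summaries of change in QTcF, Baseline is the last (or mean) QTcF before the first dose in the main study. Baseline 2 is the last QTcF before the first active dose in the extension, as in Section 6.2.2. The highest pre-dose value is used only to identify subjects who meet the protocol's existing >60 ms criterion, and their number will be tabulated by group.* The final text should commit to either last or mean for Baseline. If alignment with the main-study SAP is needed, keep change from the highest value as a labelled extra row.

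The cost is one paragraph, a reprogrammed baseline flag and one added count line, with no new data. The downsides are a less favourable mean change, a noisier baseline if the last reading is chosen over the mean, and possible loss of alignment with the main-study SAP unless the extra row is shown.

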5.5.1 Pharmacokinetics/Pharmacodynamics

Linzagolix was evaluated in a Phase 1 single/repeated-dose study (Study KLH1101) in which Japanese and Caucasian pre- and post-menopausal women received single doses of linzagolix from 12.5 to 700 mg and repeated once daily doses of 100 to 400 mg once daily for 7 days under fed and fasted conditions. Linzagolix was safe and well-tolerated, showed linear PK, a half-life of about 15–20 hours, and little difference between pre- and post-menopausal women or between Japanese and Caucasian women. There was a dose-dependent suppression of E2, LH and follicle-stimulating hormone (FSH).

Study 17-OBE2109-001 evaluated the tolerability and PK of a single supra-therapeutic dose of 700 mg linzagolix, and effects of therapeutic and suprathreshold doses of linzagolix on the QTc interval (QT interval corrected for heart rate). Subjects received a 200 mg dose of linzagolix (therapeutic target exposure), a 700 mg dose of linzagolix (suprathreshold target exposure), a 400 mg dose of moxifloxacin (positive control), and placebo with an appropriate washout. Linzagolix at 700 mg was well tolerated. A borderline effect of linzagolix on the QTc interval was identified with prolongations exceeding the threshold of concern by less than 2 msec. The categorical data for QTc showed no values greater than 480 msec and no changes greater than 30 msec following administration of the suprathreshold and therapeutic doses. Thus, based on the magnitude of the QTc prolongation, the observed effects are not considered to be clinically significant.

The open-label study, KLH1103, assessed the absorption, metabolism, and excretion of linzagolix in 6 women of non-childbearing potential. Linzagolix was the predominant component in plasma and all plasma metabolites were present at less than 10% of the total drug related exposure. Similarly, unchanged linzagolix was also a major component in urine and feces. Linzagolix was eliminated in urine (52%) and, to a lesser extent, in feces (38%).

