1.2. Objectives

The primary objective of this extension study was to assess the maintenance of efficacy of linzagolix administered orally once daily for up to an additional 6 months (for up to 12 months of treatment in total) in women who had already completed 6 months of linzagolix treatment at a dose of 75 mg alone or of 200 mg in combination with add-back therapy (estradiol (E2) 1 mg / norethisterone acetate (NETA) 0.5 mg) in the management of moderate to severe endometriosis-associated pain (EAP) in women with surgically confirmed endometriosis. The two co-primary efficacy endpoints were clinically meaningful reduction over the last 28 days of randomized treatment up to the Month 12 visit, along with a stable or decreased use of analgesics for EAP, for 1) dysmenorrhea (DYS) and for 2) non menstrual pelvic pain (NMPP).

Secondary objectives included evaluation of efficacy over the last 28 days of randomized treatment up to the Month 12 visit based on the following parameters: evaluation of pain associated with sexual intercourse (dyspareunia) and defecation (dyschezia), difficulty of doing daily activities, analgesic use, assessment of subject perception of severity, change in uterine bleeding, Quality of Life (QoL) questionnaires, pharmacoeconomic burden of endometriosis by assessing changes in patient productivity, assessment of endometriosis-related number of non-study health visits, number of days in hospital and type of medical procedures performed during the Treatment Period.

Safety and tolerability objectives included assessment of bone mineral density (BMD), endometrial health, cardiac safety including QT interval prolongation, standard laboratory safety parameters, gynecological assessments and adverse event (AE) frequency including specific hypoestrogenic AEs.

Exploratory objectives included assessment of bone turnover markers and collection of pharmacokinetic (PK) and pharmacodynamic (PD) related data of linzagolix for a separate modelling exercise.

Populations for analysis, data handling rules, statistical methods, and formats for data presentation are provided. The statistical analyses and summary tabulations described in this SAP will provide the basis for the results sections of the clinical study report (CSR) for this trial.

This SAP will also outline any differences in the currently planned analytical objectives relative to those planned in the study protocol.

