- Adverse Event
- Subject's request
- Protocol Violation

CRS-BS-TP-000005 V 2.0

Page 15 of 99

- Lost to Follow-up
- Pregnancy
- Other

Details are provided in the Protocol.

Discontinuation Rules during the Treatment Period:

Endometrial biopsies: in case of an endometrial biopsy diagnosis of endometrial hyperplasia of any type or worse, the subject was to discontinue study treatment (and was not eligible to enter the extension study) and was to be advised to undergo gynecological evaluation and treatment.

Serum calcium: Subjects with a serum calcium level on treatment above 2.9 mmol/L was to have calcium supplements interrupted. If serum calcium level on treatment was above 3.1 mmol/L, calcium supplements and study treatment were to be interrupted. A repeat test of this parameter within 2 weeks under fasting conditions was to be performed. If the results of the repeat remained above 2.9 mmol/L, study treatment was to be discontinued and the subject was to be advised to consult an endocrinologist for further evaluation.

BMD loss: subjects who experienced more than 8% BMD loss or a Z-score \leq -2.5 at any site (femoral neck, hip or spine) were to be discontinued from study treatment and were to enter the follow-up period (they were not eligible to enter the extension study).

Liver function tests: following the Food and Drug Administration (FDA) guidance on drug-induced liver injury, subjects who had an elevation of hepatic enzymes were to be withdrawn immediately from treatment if:

- ALT or AST >8xULN
- ALT or AST >5xULN for more than 2 weeks
- ALT or AST >3xULN and (TBL >2xULN or INR >1.5)

• ALT or AST >3xULN with the appearance of fatigue, nausea, vomiting, right upper quadrant pain or tenderness, fever, rash, and/or eosinophilia (>5%)

Withdrawn subjects were to be followed up until hepatic parameters returned to normal.

ECG : subjects with a QTcF > 500 ms or increase > 60 ms from the highest value prior to first dose were to be withdrawn from study treatment and followed up until return to QTcF < 480 ms or – if not reached after 3 months of treatment cessation- be referred to a cardiologist. They were to enter the 6-month Follow-Up Period and undergo follow-up ECGs according to the schedule of events.

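### QT prolongation is a named safety objective with its own withdrawal limits, but SAP 6.6.5 plans no count of the women who cross them

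*SAP*

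**What the plan says.** The safety objectives in Protocol 6.2 and SAP 1.2 include "cardiac safety including QT interval prolongation". Protocol 5.7 reports a borderline QTc effect in healthy volunteers, judged not clinically significant, and says that monthly ECGs will be done all the same.

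The withdrawal rule in Protocol 10.7.2.1 covers "subjects who have a QTcF > 500 ms or increase > 60 ms from the highest value prior to the first dose"; the dose meant is the first one of the main study. SAP 2.4 repeats both limits.

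On the earlier QT study, Protocol 5.5.1 reports: "The categorical data for QTc showed no values greater than 480 msec and no changes greater than 30 msec".

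SAP 6.6.5 sets out the data and the analysis:
- "Local 12-lead ECG readings of QTcF are performed at every monthly visit during the extension treatment period", and again at follow-up Months 1, 3 and 6.
- "Baseline will be defined as the highest QTcF value prior to first dose of the main study". For ex-placebo women only, there is also a baseline 2, the highest value from screening to Month 6.
- Descriptive summaries are planned for actual values and for changes from both baselines.
- There is one categorical output: "as well as the number and percent of subjects with normal, abnormal and clinically significant abnormal results at each study visit by treatment group".
- Every ECG is listed by subject.

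SAP 6.2.1 defines a continuous summary as n, mean, SD, median, quartiles, minimum and maximum, for changes as well as values.

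**The concern.** The trial names QT prolongation as a question, sets two numerical limits for it, and defines the ECG baseline as the reference that the 60 ms rule needs. The SAP then never tabulates either limit. The only categorical ECG output is the normal/abnormal call, which mixes QT with every other ECG finding.

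QT risk shows as a few women with large values, so the natural summary is a count of women. Without one, the report would describe the distribution of QTcF visit by visit. It would not state how many women in each group reached the trial's own limits over the treatment period.

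**Working it through.** **1. Group sizes.** Protocol 13.2 and SAP 6.1 start from 450 randomised women. 450 × 0.80 = 360 completers and 360 × 0.80 = 288 entrants, which reproduces the plan's figure. Assuming equal entry from the three main-study arms, 288/3 = 96 per continuing group. The 1:1 split of the former placebo arm gives 96/2 = 48 per ex-placebo group. Since 288 is stated as an upper figure, real groups may be smaller.

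**2. What a by-visit summary says about the number of women.** If the maximum change at a visit exceeds 60 ms and the third quartile does not, the number of women above 60 ms is:
- at least 1;
- at most 25% of the group: 0.25 × 96 = 24, or 0.25 × 48 = 12.

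The mean and SD narrow this range but do not in general give the count. Maxima at successive visits cannot be combined either: the same woman may supply all of them, or a different woman each time.

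**3. Which ECGs reach the visit tables.** Under SAP 5.5 (other safety data), an unscheduled ECG goes to a planned visit within ±14 days only if that visit has none. Early-discontinuation ECGs follow a similar rule. An ECG is planned at every visit, so the slot is usually filled. For example, take a Month 8 ECG on Day 225 and an unscheduled one seven days later, on Day 232. Day 232 is 7 days from Month 8, which is occupied, and 253 − 232 = 21 days from Month 9, outside the window. It would appear in the listing but in no table.

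**4. What a count would give.** One woman is 1/96 = 1.0% or 1/48 = 2.1%. With no events, the one-sided 95% upper limit is 1 − 0.05^(1/n): 3.1% for n = 96 and 6.1% for n = 48.

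**5. Whether one or several is a live question.** With P(≥1) = 1 − (1 − p)^n and P(≥2) = P(≥1) − np(1 − p)^(n−1), and an assumed true rate p from 0.5% to 2% (the documents give none):

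| n | P(at least 1) | P(at least 2) |
|---|---|---|
| 96 | 38% to 86% | 8% to 57% |
| 48 | 21% to 62% | 2% to 25% |

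**6. How the SAP treats other safety measures.**

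| Measure | Planned threshold or worst-value output |
|---|---|
| BMD (6.6.2) | Categories of percent loss, including above 8%, its withdrawal limit |
| Liver tests (6.6.3) | Shift to worst on-treatment value, unscheduled tests included |
| Progesterone (6.6.3) | Proportion above 10 nmol/L at least once, Month 6 to 12 |
| QTcF (6.6.5) | None |

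The QTcF limits are programmed at Month 6 (SAP 4.1), but only to derive analysis sets. The disposition table (SAP 6.3.1) has a single line for women who met discontinuation criteria at Month 6, not split by criterion.

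**The case against.** The strongest reply is that the planned outputs already reveal outliers. The ECG baseline matches the 60 ms rule, so a maximum change above 60 ms, or a maximum value above 500 ms, shows directly that a limit was crossed at that visit. Every ECG is listed. A woman who crosses must stop treatment, and Protocol 12.1.2 names an abnormality that leads to discontinuation as one to report as an adverse event. She should then appear among events leading to discontinuation, which SAP 6.6.1 counts and lists. The DMC reviews ECG parameters. The protocol's ECG endpoint is change from baseline at scheduled assessments, and the SAP delivers that.

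Most of this stands. A reader might infer that the SAP tabulates only mean change, that outliers cannot be seen, or that the trial has no means of finding who crossed. SAP 6.2.1 and the listing in 6.6.5 contradict all three. A reader might also infer that the earlier QT signal was set aside on categorical counts alone. Protocol 5.5.1 rests its conclusion on the size of the prolongation and also cites an exceedance of less than 2 msec.

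What does not stand is that these outputs replace a count. The adverse-event route depends on reporting and carries no QTcF value. It also need not catch a crossing at Month 12, when treatment has already ended (Protocol 10.2.1). Exit reasons have no QT category. Counting by hand from a full listing is possible, but it is not a planned result.

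**Conclusion.** The point holds as a reporting gap on a stated objective, and it is a cheap improvement. The SAP plans no number and percent of women above 500 ms or with a rise above 60 ms, at each visit or as a worst on-treatment value. Crossings can be found only from by-visit maxima, which do not count women and can miss unscheduled or withdrawal ECGs, and from the listing.

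No data are lost, no prespecified endpoint is broken, and no sample size, test or clinical rule is affected. The percentages and upper limits in the working rest on 288 entrants and equal entry by arm; smaller groups would give wider limits. The absence of the table does not depend on any assumption.

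**What to change.** Add to SAP 6.6.5, on the Extension Safety Analysis Set and by the four treatment groups, one table with each woman counted once at her worst on-treatment ECG, including unscheduled and withdrawal ECGs. Give n and % with:
- any QTcF above 480 ms, and above 500 ms;
- any increase above 30 ms, and above 60 ms, from the highest pre-dose value (the SAP's ECG baseline).

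For ex-placebo women, repeat the increases against baseline 2. Its look-back includes the main baseline period, so it is never lower than baseline, and counts against it can only be equal or smaller.

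Define the window from the first extension dose through the Month 12 or withdrawal ECG. The treatment period in SAP 5.2.1 ends the day before the Month 12 visit and, taken literally, would drop that ECG. Add a subset listing of women above 500 ms or 60 ms.

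All four cut-offs come from Protocol 5.5.1 and 10.7.2.1 and serve only for tabulation. Protocol 5.5.1 states its two for QTc without naming the correction, so the table should say that it applies them to QTcF.

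The cost is one table and one short listing from data already collected, and one more safety output to review. If the SAP can no longer be amended before database lock, the table can be reported as an addition and labelled so.
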